### 7.3.1 Anorexia/Weight loss

Selinexor treatment can lead to anorexia, decreased food intake with subsequent weight loss. Participants should be weighed at least weekly during study-required outpatient visits during cycle 1 and biweekly during cycles 2 and 3. If the patient is admitted for dehydration or malnutrition, more frequent weight assessment is recommended. It is strongly recommended that patients receive ongoing nutritional assessment and dietary support consultation. Administration of high caloric beverages (e.g., Pediasure®) should be considered for all patients. The use of supplemental tube feeding is acceptable.

Patients who experience decreased food/liquid/caloric intake secondary to anorexia should have a patient log of food and drink with monitoring by the treatment team. Fresh juices, simple carbohydrates, as well as ginger-containing foods and beverages can improve appetite.

Supportive care should be escalated for  $\geq$  Grade 1 anorexia or weight loss. **Guidelines for standard appetite stimulants are provided in the table below. The use of low dose olanzapine has been the most helpful in the control of nausea and anorexia in adult studies using selinexor.** Olanzapine for appetite stimulation and the treatment of chemotherapy induces nausea and vomiting, has not been thoroughly studied in children, and may have overlapping side effects with selinexor, including sedation and dizziness. For pediatrics, the suggested starting dose of olanzapine is approximately 0.06 mg to 0.1 mg/kg for patients < 10 years, 1.25 mg PO qPM for patients 10 – 12 years old or 2.5 mg PO qPM for patients > 12 years old. Patients who exhibit no response after 4 weeks, defined as no weight gain or further loss, may increase by 1.25 mg/day weekly to maximum 2.5 mg/day for children < 10 years, 5 mg/day for children ages 10 – 12, and 10 mg/day for children older than 12 years; use caution escalating olanzapine doses in patients younger than 10 years. Olanzapine may be given in combination with a corticosteroid. Either dexamethasone < 0.25 mg/kg daily (max dose: 10 mg) or prednisone < 0.5 mg/kg daily (max dose: 20 mg) is recommended on the days of, and 1 day after, selinexor dosing.

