Accrual to Parts B and C will only open once the MTD or recommended phase 2 dose has been determined in Part A, and may open concurrently with the PK expansion described above.

A maximum of 24 patients are expected to enroll in Parts B and C combined, assuming an inevaluability rate of 20%. We anticipate that each part of the study will require 6-12 months for enrollment.

Response for Part B will be defined as either MR, PR or CR on two consecutive 2D measurements on standard imaging done 4 weeks apart (See [Section 12.6](#)). Sustained responses are very rare in this cohort of recurrent non-DIPG HGGs. We will consider the agent of sufficient interest for further evaluation in this disease category if at least one PR or CR, or at least two MRs, is observed among 10 enrolled patients. A response rate of 20% or more would be evidence of sufficient activity. If the true response rate is 20%, then the probability of observing one or more responses among 10 evaluable patients is about 89.3%. If the response rate is 5%, then the probability of observing at least one response is about 40.1%.

Clinical benefit for Part C will be evaluated separately using the criteria of no visible disease progression six months from the start of treatment. If two or more of a cohort of up to six patients are unable to resume therapy within 6 weeks after surgery, the surgical arm will be declared not feasible. If Part B has fully accrued, Part C will close to further accrual.

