#### 12.6.4 Response Criteria for Target Lesions

THIS PROTOCOL IS FOR RESEARCH PURPOSES ONLY, SEE PAGE 1 FOR USAGE POLICY

Response criteria are assessed based on the product of the longest diameter and its longest perpendicular diameter. Development of new disease or progression in any established lesions is considered progressive disease, regardless of response in other lesions – e.g., when multiple lesions show opposite responses, the progressive disease takes precedence. Response Criteria for target lesions:

- **Complete Response (CR)**: Disappearance of all target lesions.
- **Partial response (PR)**:  $\geq 50\%$  decrease in the sum of the products of the two perpendicular diameters of all target lesions (up to 5), taking as reference the initial baseline measurements.
- **Minor Response (MR)**: A greater than or equal to 25% but less than 50% reduction in the product of the greatest tumor diameter and its perpendicular diameter on MRI scan, on a stable or decreasing dose of steroids with a stable or improving neurologic examination.
- **Stable Disease (SD)**: Neither sufficient decrease in the sum of the products of the two perpendicular diameters of all target lesions to qualify for PR, nor sufficient increase in a single target lesion to qualify for PD.
- **Progressive Disease (PD)**: 25% or more increase in the sum of the products of the perpendicular diameters of the target lesions, taking as reference the smallest sum of the products observed since the start of treatment, or the appearance of one or more new lesions.

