#### 12.6.7 Overall Response Assessment

The overall response assessment takes into account response in both target and non-target lesions, the appearance of new lesions and normalization of markers (where applicable), according to the criteria described in the table below. The overall response assessment is shown in the last column, and depends on the assessments of target, non-target, marker and new lesions in the preceding columns.

Target Lesions	Non-target Lesions	Markers	New Lesions	Overall Response
CR	CR	Normal	No	CR
CR	IR/SD	Normal	No	PR
CR	CR, IR/SD	Abnormal	No	PR
PR	CR, IR/SD	Any	No	PR
MR	CR, IR/SD	Any	No	MR
SD	CR, IR/SD	Any	No	SD
PD	Any	Any	Yes or No	PD
Any	PD	Any	Yes or No	PD
Any	Any	Any	Yes	PD

Each patient will be classified according to his “best response” for the purposes of analysis of treatment effect. Best response is determined as outlined in Section 12.7.1 from a sequence of overall response assessments.

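### The steroid and neurologic conditions guard minor response but not PR or CR in CNS tumors, although one PR or CR alone meets the Part B go rule

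*Combined protocol and SAP*

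**What the plan says.** Section 12.6.4 defines the CNS response categories for target lesions.

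- CR is "Disappearance of all target lesions".
- PR is a decrease of at least 50% in the "sum of the products of the two perpendicular diameters of all target lesions (up to 5), taking as reference the initial baseline measurements".
- MR is a decrease of at least 25% but under 50%, and it alone must be seen "on a stable or decreasing dose of steroids with a stable or improving neurologic examination".

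The overall assessment in Section 12.6.7 "takes into account response in both target and non-target lesions, the appearance of new lesions and normalization of markers". Steroid dose and clinical status are not among its elements.

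Section 11.1 refers Part B response to Section 12.6, requires it "on two consecutive 2D measurements on standard imaging done 4 weeks apart", and declares sufficient interest "if at least one PR or CR, or at least two MRs, is observed among 10 enrolled patients". Section 11.2.3 adds that a CR or PR counts for this rule once central review confirms it. Section 11.1 also brings into the rule those Part A patients who meet Part B eligibility and are evaluable for response.

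Steroids appear in the supportive-care text in several places: as one possible second antiemetic (Section 5.3.1), for symptomatic patients in general (7.3), with 5-HT3 antagonists (7.3.2.1), for anorexia (7.3.1) and for fatigue or somnolence (7.3.6). In Section 7.3.1 a corticosteroid may be paired with olanzapine, and where it is, a low dose "is recommended on the days of, and 1 day after, selinexor dosing".

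**The concern.** By attaching a steroid condition to MR, the plan accepts that a change in steroid dose can alter the measured size of these tumors. It then leaves the condition off the two categories that carry more weight. Read literally, a 45% decrease on a rising steroid dose is not an MR, but a 50% decrease on the same rising dose, or with a worsening neurologic examination, is a PR. That single PR settles Part B, whereas two guarded MRs would be needed for the same conclusion. Nothing in the documents explains this ordering.

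At stake is the Part B conclusion that the agent merits further evaluation in high-grade glioma. The Part B clinical-benefit rate in Section 11.5 also uses PR and CR.

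**Working it through.** **1. The definitions side by side (Sections 12.6.4 and 11.1)**

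| Category | Measured decrease | Steroid condition | Neurologic condition | Number that meets the Part B rule |
|---|---|---|---|---|
| CR | all target lesions gone | none | none | 1 PR or CR |
| PR | at least 50% | none | none | 1 PR or CR |
| MR | at least 25%, under 50% | yes | yes | 2 |

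**2. Does another section supply the condition for PR or CR?**

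- Section 4.2.2.1 requires a stable or decreasing corticosteroid dose for 7 days, but before enrollment only.
- Section 8.1 schedules neurologic examinations. Its table has no item for steroid dose at tumor evaluation.
- Sections 8.2.1 and 11.2.3 require central review of images and give no steroid criterion.
- Section 11.1 requires confirmation after 4 weeks and does not mention steroids.
- Sections 12.6.7 and 12.7.1 combine lesion, marker and confirmation results only.

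None supplies it.

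**3. The plan's own figures (Section 11.1, n = 10)**

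P(at least one response) = 1 − (1 − rate)^10

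- Rate 20%: 1 − 0.80^10 = 1 − 0.1074 = 0.8926. The plan states 89.3%.
- Rate 5%: 1 − 0.95^10 = 1 − 0.5987 = 0.4013. The plan states 40.1%.

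Both reproduce, and neither is in dispute here.

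**4. How sensitive the rule is, under assumed rates**

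Let p be the true PR/CR rate. Let q be the chance that a patient without a true response shows a decrease of at least 50% that is due to steroids, holds on two scans 4 weeks apart and passes central review. The documents give no value for q, so those below are assumptions. The route through two MRs is left out.

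Counted rate r = p + (1 − p)q, and P(at least one counted PR or CR in 10) = 1 − (1 − r)^10.

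| q (assumed) | p = 0 (inactive drug) | p = 5%: r | p = 5%: probability |
|---|---|---|---|
| 0 | 0% | 0.0500 | 40.1% |
| 1% | 1 − 0.99^10 = 9.6% | 0.0595 | 45.9% |
| 2% | 1 − 0.98^10 = 18.3% | 0.0690 | 51.1% |
| 5% | 1 − 0.95^10 = 40.1% | 0.0975 | 64.2% |

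At p = 5% the increase over 40.1% is about 6, 11 and 24 percentage points. At p = 20% the probability moves from 89.3% to 90.3%, 91.2% and 93.6%, so the effect falls mainly on the false-positive side.

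**5. Timing of the short courses**

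Dosing under Amendment #4 is on Days 1, 8, 15 and 22. A course covering the dose day and the next day, as in Section 7.3.1, last ends on Day 22 + 1 = Day 23. The scan is at the end of a 28-day cycle, so such a course alone would have ended about 5 days before a Day 28 scan.

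**The case against.** The strongest reply is that the plan does have checks. A Part B response must appear on two scans 4 weeks apart. Section 8.1 calls for a repeat evaluation on the next cycle after a first PR or CR. Central review must confirm the PR or CR. Steroids must be stable or falling before enrollment, and clinical progression ends protocol therapy under Section 10.1. This stands as far as it goes: a brief fluctuation is unlikely to pass. It does not close the gap, because a raised dose can persist through both scans and no step tells anyone to discount it.

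A reader might infer that the protocol prescribes corticosteroids around every dose. It does not. Section 7.3 says its recommendations are not required, and the sentence quoted from Section 7.3.1 applies only where a corticosteroid is added to olanzapine. The timing in step 5 also shows that such a course need not be running at the scan. The documents show that steroid changes are allowed and foreseeable, not that they are routine at evaluation.

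A reader might also infer that steroid dose goes unrecorded. That cannot be established: Section 14.1 places the case report forms in a separate packet, and MR cannot be assigned without the dose. The reviewers' instructions are likewise not in the documents.

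Finally, Part B response is a secondary aim, and Section 11.5 describes these analyses as exploratory. That limits the stakes, but the go criterion is explicit and a PR should mean the same thing for every patient it counts.

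**Conclusion.** The asymmetry is plain on the text: only MR carries the steroid and neurologic conditions, and one unguarded PR or CR meets a rule that needs two guarded MRs. Confirmation and central review reduce the risk of counting a steroid-driven PR without removing it.

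The size of the bias cannot be derived from the documents. The probabilities of 9.6%, 18.3% and 40.1% rest on an inactive drug, independent patients and assumed confirmed rates of 1%, 2% and 5%. They show how sensitive a one-in-ten rule is. A reader might take them as estimates of how often Part B will mislead, and the documents do not support that use.

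This is a gap in an endpoint definition that should be closed. It is not an error in any stated figure.

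**What to change.** In Section 12.6.4:

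1. Require for CNS PR and CR what MR already requires: a steroid dose that is stable or decreasing relative to the baseline scan, and a stable or improving neurologic examination.
2. State that a measured decrease that fails this condition is classified as SD, and adjust the SD wording. Otherwise a decrease of 50% or more on rising steroids fits no category: it would fail PR, it lies above the MR range, and SD is worded as an insufficient decrease.
3. State how short intermittent supportive-care courses count, for response classification only.

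Elsewhere:

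4. Make the steroid dose at each tumor evaluation available to the response assessment, including central review.
5. Apply the same rule to the Part A patients who count in the Part B rule under Section 11.1.

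The cost is a few lines of text and one steroid-dose item per evaluation, if the separate forms do not already hold it. Neurologic examinations are already scheduled. For Part A patients already treated, the dose may have to be taken from source records, so this is best settled before the go rule is applied. The downside is that an occasional PR on rising steroids is downgraded. No change to steroid use or patient management is implied.

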#### 12.6.5 Response Criteria for Non-Target Lesions:

- **Complete Response (CR)**: Disappearance of all non-target lesions.
- **Incomplete Response/Stable Disease (IR/SD)**: The persistence of one or more non-target lesions.
- **Progressive Disease (PD)**: The appearance of one or more new lesions and/or unequivocal progression of existing non-target lesions.

#### 12.6.6 Response criteria for tumor markers (if available):

Tumor markers will be classified simply as being at normal levels or at abnormally high levels.

#### 12.6.7 Overall Response Assessment

The overall response assessment takes into account response in both target and non-target lesions, the appearance of new lesions and normalization of markers (where applicable), according to the criteria described in the table below. The overall response assessment is shown in the last column, and depends on the assessments of target, non-target, marker and new lesions in the preceding columns.

Target Lesions	Non-target Lesions	Markers	New Lesions	Overall Response
CR	CR	Normal	No	CR
CR	IR/SD	Normal	No	PR
CR	CR, IR/SD	Abnormal	No	PR
PR	CR, IR/SD	Any	No	PR
MR	CR, IR/SD	Any	No	MR
SD	CR, IR/SD	Any	No	SD
PD	Any	Any	Yes or No	PD
Any	PD	Any	Yes or No	PD
Any	Any	Any	Yes	PD

Each patient will be classified according to his “best response” for the purposes of analysis of treatment effect. Best response is determined as outlined in Section 12.7.1 from a sequence of overall response assessments.

## 12.7 Best Response

### 12.7.1 Evaluation of Best Overall Response

The best overall response is the best response recorded from the start of the treatment until disease progression/recurrence (taking as reference for progressive disease the smallest measurements recorded since the treatment started). The patient's best response assignment will depend on the achievement of both measurement and confirmation criteria.

Table 1: For Patients with Measurable Disease (i.e., Target Disease)

Target Lesions	Non-Target Lesions	New Lesions	Overall Response	Best Overall Response when Confirmation is Required*
CR	CR	No	CR	≥28 days Confirmation**
CR	Non-CR/Non-PD	No	PR	≥28 days Confirmation**
CR	Not evaluated	No	PR	
PR	Non-CR/Non-PD/not evaluated	No	PR	
SD	Non-CR/Non-PD/not evaluated	No	SD	documented at least once ≥28 days from baseline**
PD	Any	Yes or No	PD	no prior SD, PR or CR
Any	PD***	Yes or No	PD	
Any	Any	Yes	PD	

\* See RECIST 1.1 manuscript for further details on what is evidence of a new lesion.  
 \*\* Only for non-randomized trials with response as primary endpoint.  
 \*\*\* In exceptional circumstances, unequivocal progression in non-target lesions may be accepted as disease progression.  
 Note: Patients with a global deterioration of health status requiring discontinuation of treatment without objective evidence of disease progression at that time should be reported as “symptomatic deterioration.” Every effort should be made to document the objective progression even after discontinuation of treatment.

Table 2: For Patients with Non-Measurable Disease (i.e., Non-Target Disease)

Non-Target Lesions	New Lesions	Overall Response
CR	No	CR
Non-CR/non-PD	No	Non-CR/non-PD*
Not all evaluated	No	not evaluated
Unequivocal PD	Yes or No	PD
Any	Yes	PD

\* 'Non-CR/non-PD' is preferred over 'stable disease' for non-target disease since SD is increasingly used as an endpoint for assessment of efficacy in some trials so to assign this category when no lesions can be measured is not advised

Table 3. Sequences of overall response assessments with corresponding best response.

1 st Assessment	2 nd Assessment	Best Response
Progression		Progressive disease
Stable, PR, CR	Progression	Progressive disease
Stable	Stable	Stable
Stable	PR, CR	Stable
Stable	Not done	Not RECIST classifiable
PR	PR	PR
PR	CR	PR
PR, CR	Not done	Not RECIST classifiable
CR	CR	CR

Table 4: Overall Response for Patients with Neuroblastoma and Measurable Disease

CT/MRI	MIBG	Bone Scan	Bone Marrow	Catechol	Overall
PD	Any	Any	Any	Any	PD
Any	PD	Any	Any	Any	PD
Any	Any	PD	Any	Any	PD
Any	Any	Any	PD	Any	PD
SD	CR/PR/SD	Non-PD	Non-PD	Any	SD
PR	CR/PR	Non-PD	Non-PD	Any	PR
CR/PR	PR	Non-PD	Non-PD	Any	PR
CR	CR	Non-PD	Non-PD	Elevated	PR
CR	CR	CR	CR	Normal	CR

Table 5: Overall Response Evaluation for Neuroblastoma Patients and MIBG Positive Disease Only

If patients are enrolled without disease measurable by CT/MRI, any new or newly identified lesion by CT/MRI that occurs during therapy would be considered progressive disease.

MIBG	CT/MRI	Bone Scan	Bone Marrow	Catechol	Overall
PD	Any	Any	Any	Any	PD
Any	New Lesion	Any	Any	Any	PD
Any	Any	PD	Any	Any	PD
Any	Any	Any	PD	Any	PD
SD	No New Lesion	Non-PD	Non-PD	Any	SD
PR	No New Lesion	Non-PD	Non-PD	Any	PR
CR	No New Lesion	Non-PD	Non-PD	Elevated	PR

CR	No New Lesion	CR	CR	Normal	CR
----	---------------	----	----	--------	----

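### Section 12.7.1 gives two different best responses for a patient who has SD, PR or CR and then progresses; only the descriptive best-response summary is affected

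*Combined protocol and SAP*

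**What the plan says.** The lead sentence of Section 12.7.1 reads: "The best overall response is the best response recorded from the start of the treatment until disease progression/recurrence". The next sentence adds: "The patient's best response assignment will depend on the achievement of both measurement and confirmation criteria".

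Table 1 (measurable disease) sets conditions for each category. PD as best response requires "no prior SD, PR or CR". SD must be "documented at least once ≥28 days from baseline", and CR and PR need confirmation after at least 28 days. The CR, PR and SD conditions carry a double-asterisk footnote: "Only for non-randomized trials with response as primary endpoint". The PD condition does not.

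Table 3 is titled "Sequences of overall response assessments with corresponding best response". One row, read across, is "Stable, PR, CR Progression Progressive disease". Other rows score Stable followed by PR or CR as Stable, and Stable followed by no second assessment as not RECIST classifiable. The table has two assessment columns and no third.

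Sections 12.2.5, 12.3.6, 12.5.2 and 12.6.7 all send patients to 12.7.1 for the classification used in the analysis of treatment effect. For CNS tumors, Section 12.6.7 says: "Best response is determined as outlined in Section 12.7.1 from a sequence of overall response assessments". Its per-visit table has an MR row; Tables 1 and 3 of 12.7.1 have none.

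**The concern.** Two analysts applying Section 12.7.1 to the same scans can report different best-response distributions, each citing the protocol. Patients with SD who progress at the next evaluation are the critical group. Section 11.1 describes sustained responses as very rare in recurrent non-DIPG high-grade glioma, so the split between SD and PD may carry much of what the summary shows. With no stated precedence, the choice between tables could be made after the data are seen. The summary serves the secondary aim of describing antitumor effect (1.2.1).

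**Working it through.** **Plan's own figure.** The tables carry no figure. The only response calculation in the plan is for Part B in Section 11.1, and it reproduces: 1 − 0.80^10 = 0.893 and 1 − 0.95^10 = 0.401, against the stated 89.3% and 40.1%. It rests on the response definition in 11.1, not on these tables.

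**Sequences side by side.**

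| Assessments in order | Lead sentence and Table 1 | Table 3 |
|---|---|---|
| SD, PD | SD (Table 1 adds 28 days or more from baseline, if that applies) | PD |
| PR or CR, PD | PR or CR if confirmation is not required; if it is required and unmet, the prior response still rules out PD | PD |
| SD, PR or CR | PR or CR if confirmation is not required; SD if it is required and still pending | Stable |
| SD, PR or CR, then confirmed | PR or CR | No row; Stable if the first two columns are read literally |
| SD, not done | SD, since one documentation is enough | Not classifiable |
| SD then MR; MR then SD, MR, PR or CR | No MR row in Table 1 | No row |

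The first two lines are direct contradictions. The fourth and sixth are gaps. The fifth is a mismatch. The third depends on whether confirmation is required.

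**Does the 28-day SD condition remove the first conflict?** Baseline imaging is taken 0 to 14 days before treatment starts, and the first evaluation is at the end of a 28-day cycle (Section 8.1). A scan at the start of Cycle 2 is therefore 28 to 28 + 14 = 42 days from baseline. If the 72-hour window before the next cycle is used in full, the lower end is 28 − 3 = 25 days. The condition will usually be met. By its footnote it may not apply here at all, because response is a secondary aim (Section 1.2). If it does not apply, the lead sentence still conflicts with Table 3.

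**Supporting text.** Section 12.7.2 times stable disease from the start of treatment to progression. That presupposes that SD followed by progression is still SD.

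**Size.** Let k of n patients go from SD (meeting any SD minimum) to PD at the next assessment. Among these patients the SD count is k under Table 1 and 0 under Table 3, so the SD rates differ by k/n. The documents give no k. With n = 10 and assumed k = 2, 4 or 6, the gap is 2/10, 4/10 or 6/10, that is 20, 40 or 60 percentage points.

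**The case against.** The strongest reply is that little depends on these tables. Section 11.1 defines Part B response itself, as MR, PR or CR on two consecutive two-dimensional measurements 4 weeks apart. Section 11.5 defines clinical benefit as PR or CR on two consecutive measurements or more than 12 weeks without progression (Part B), and as no visible progression at six months (Part C). It calls these analyses descriptive and exploratory. No disease-control rate based on best response is defined. All of this stands and sets the limit of the point.

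A reader might go further and infer that the Part B decision changes with the table used. For example, if half of the responders at a true 20% rate first respond after an SD scan and are scored Stable, the chance of at least one response in 10 would fall from 89.3% to 1 − 0.90^10 = 65.1%. That requires Table 3 to replace the Section 11.1 definition, and no text does so.

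Two other strong readings also fail. Scoring Stable then PR or CR as Stable is a fair treatment of a response not yet confirmed, and further imaging after a first PR or CR is already required (Section 8.1, footnote 3; Section 12.2). The defect is only that Table 3 has nowhere to record the confirmation. Nor is MR undefined: it appears in 12.6.4, 12.6.7, 12.7.2 and 11.1. The SD definition in 12.6.4, set only against PR and PD, would even absorb an MR. What is missing is an MR category in the best-response tables.

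None of this answers the conflict over SD, PR or CR followed by progression.

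**Conclusion.** Section 12.7.1 is wrong as written. Its lead sentence and Table 1 exclude PD as best response after an earlier SD, PR or CR, Table 3 assigns it, and neither is given precedence. The SD rate in the best-response summary can differ by k/n on identical data; the 20, 40 and 60 points are illustrations, because k is an assumption. The missing row for a late confirmed response, the treatment of a single SD assessment and the missing MR rows are lesser faults in the same tables.

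The effect is confined to a secondary, descriptive summary. The documents do not support extending it to the dose-finding conclusion, the Part B activity rule or the clinical benefit endpoints. The tables should be repaired before the summary is produced.

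**What to change.** 1. State that the lead sentence of 12.7.1 governs. State also whether the double-asterisk conditions (confirmation of CR and PR, and the SD minimum) apply to this trial, given that response is a secondary aim. Settle this first, because items 2 to 4 depend on it.
2. Split the Table 3 row for SD, PR or CR followed by progression. SD then progression becomes SD, subject to the SD minimum if it applies. PR or CR then progression becomes PR or CR if confirmation is not required, or SD if it is required and was not met before progression.
3. Add a row crediting Stable, then PR or CR, then confirmed PR or CR, as PR or CR.
4. Align the row for Stable with no second assessment with Table 1, which accepts SD documented once.
5. Add MR rows for CNS tumors, using the two-consecutive-measurement definition of Section 11.1 for Part B.

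Items 1 to 4 are rewording and need no new data. For item 5, the early repeat scan in Section 8.1 is triggered only by PR or CR, so the text should say that MR is confirmed from the scans available.
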